Based on this hypothesis, i.e., the lower end of the 95% confidence interval for antibody protection level ratio (experimental group/control group) > 0.8 , assuming that type I error is 0.025 (one-sided), study power is 90%, estimated antibody protection level ratio (experimental group/control group) on Study Day 15 of administration is 1, estimated protection level of control group is 98.7%, distribution ratio of samples is 3:1 (experimental group/control group), and sample exclusion rate is 20%, 52 samples will be required (39 samples for experimental group and 13 samples for control group). The existing 1,000 cases will ensure a test power of 100% when the hypotheses remain unchanged.

- 3) AUEC₁₋₁₅ of RVNA GMC of SYN023+rabies vaccine is superior to that of HRIG+rabies vaccine (the lower end of the 95% confidence interval for RVNA GMC

$AUEC_{1-15}$ (experimental group/control group) > 1.1 .

Based on this hypothesis, i.e., the lower limit of the 95% confidence interval of the $AUEC_{1-15}$ (experimental group/control group) for the GMC of RVNA from Study Day 1 to Day 15 should be >1.1 , it is assumed that Type I error is 0.025 (one-sided) and the test power is 90%; the estimated value of $AUEC_{1-15}$ (experimental group/control group) for the GMC of RVNA from Study Day 1 to Day 15 is 147.55%, and CV% is 142%; and the randomization of the experimental group/control group is 3:1. Therefore, 900 cases are needed, including 675 cases in the experimental group and 225 cases in the control group, given a drop-out rate of 20%. The existing 1,000 cases will ensure a test power of 96.9% when the hypotheses remain unchanged.

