13.5 Statistical Analysis

13.5.1 General Principle

All statistical analyses are done with SAS 9.4 or updated versions.

Unless specifically stated, all tests are performed at the two-sided alpha level of 0.05 with 95% confidence interval.

For continuous variables, descriptive statistics include the number of non-missing values,

the mean, median, quartile, and standard deviation, maximum and minimum values. For categorical variables, descriptive statistics include frequency and composition or incidence. Unless otherwise stated, missing values will not be included in the calculation of percentage.

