Based on the study hypothesis, the lower limit of the 95% confidence interval (CI) of the geometric mean concentration of RVNA (test group/control group) is > 0.8 , a final sample size of 308 subjects (231 subjects in the test group and 77 subjects in the control group) is required with a type I error of 0.025 (one-sided), a power of 90%, an estimated geometric mean concentration of RVNA (test group/control group) on Day 99 post-dose of 86.94, and a CV of 17.32%, when assigning the subjects to the test group/control group at a ratio of 3:1 and considering a dropout rate of 20%. The current 1000 subjects are sufficient to ensure a 100% power under the same hypothesis.

- 3) The test group is non-inferior to the control group in the antibody positive rate of RVNA ($RVNA \geq 0.5$ IU/mL) on Day 99 post-dose (the lower limit of 95% CI of RVNA positive rate (test group/control group) > 0.9)

Based on the study hypothesis, the lower limit of the 95% CI of the ratio of antibody positive rates (test group/control group) is > 0.9 , a final sample size of 52 subjects (39 subjects in the test group and 13 subjects in the control group) is required with a type I error of 0.025 (one-sided), a power of 90%, an estimated ratio of antibody positive rates (test group/control group) on Day 99 post-dose of 1, and a CV of 98.7%, when assigning the subjects to the test group/control group at a

ratio of 3:1 and considering a dropout rate of 20%. The current 1000 subjects are sufficient to ensure a 100% power under the same hypothesis.

4) The SYN023 plus Rabies Vaccine group is superior to the HRIG plus Rabies Vaccine group in AUEC₁₋₁₅ of RVNA GMC (the lower limit of 95% CI of AUEC₁₋₁₅ ratio of RVNA GMC (test group/control group)>1.1)

Based on the study hypothesis, the lower limit of the 95% CI of AUEC₁₋₁₅ ratio of RVNA GMC (test group/control group) is > 1.1, a final sample size of 900 subjects (675 subjects in the test group and 225 subjects in the control group) is required with a type I error of 0.025 (one-sided), a power of 90%, an estimated AUEC₁₋₁₅ ratio of RVNA GMC (test group/control group) post-dose of 147.55%, and a CV of 142%, when assigning the subjects to the test group/control group at a ratio of 3:1 and considering a dropout rate of 20%. The current 1000 subjects are sufficient to ensure a 96.9% power under the same hypothesis.

2 General Statistical Considerations

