2.3.4 Handling Rules of Missing Data

Missing data are not planned to be handled in this study, unless otherwise specified.

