2.3.5 Handling of RVNA Data Below the Lower Limit of Quantitation (BLQ)

For BLQs of RVNA data, they will be calculated as zero if the samples are collected prior to the injection date of investigational product, otherwise, they will be treated as missing data and will not be included in the analysis.

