2.4 Multiplicity Comparison

Based on multiple hypothesis testing in this study, testing of superiority of the test group over the control group in the geometric mean concentration of RVNA on Day 8 post-dose will be performed at the 0.025 (one-sided) level (testing of primary study hypothesis);

If the primary hypothesis testing is successful, testing of superiority of the test group over the control group in the geometric mean concentration of RVNA on Day 4 post-dose will be performed at the 0.025 (one-sided) level (testing the secondary hypothesis 1), otherwise, testing of all 4 secondary hypotheses will be performed for exploratory analyses;

If the secondary hypothesis testing 1 is successful, testing of non-inferiority of the test group over the control group in the geometric mean concentration of RVNA on Day 99 post-dose (test for the secondary hypothesis 2) will be performed at a level of 0.025 (one-sided), otherwise, testing of secondary hypotheses 2, 3 and 4 will be performed for exploratory analyses;

If the secondary hypothesis testing 2 is successful, testing of non-inferiority of the test group over the control group in antibody positive rate of RVNA ($RVNA \geq 0.5$ IU/mL) on Day 99 post-dose (testing of the secondary hypothesis 3) will be performed at a level of 0.025 (one-sided), otherwise, testing of secondary hypotheses 3 and 4 will be performed for exploratory analyses;

If the secondary hypothesis testing 3 is successful, testing of superiority of the SYN023 plus Rabies Vaccine over the HRIG plus Rabies Vaccine in AUEC₁₋₁₅₀ of

RVNA GMC will be performed at a level of 0.025 (one-sided) (testing of the secondary hypothesis 4), otherwise, testing of secondary hypotheses 4 will be performed for exploratory analysis.

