3.2.2.2.1 Primary Analysis

The positive rates of RVNA on Days 4, 8, 15, 43, 99, 183, and 365 post-dose will be described by the number and percentage of subjects, and the inter-group differences will be compared using a chi-square test or an exact probability test (expected value < 5 in either cell), and inter-group differences in positive rates and their 95% CIs will be calculated based on Wald or Clopper-Pearson.

In addition, rate differences and P-values adjusted for the stratification factor of study site will be calculated using the CMH. A bar graph of RVNA concentrations will be created by scheduled visits.

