3.2.2.2.3 Sensitivity Analysis

Based on the PPS only, a sensitivity analysis will be performed after excluding the deviations in post-dose RVNA from geometric mean concentration \pm 3 times the geometric SD using the same method as the primary analysis.

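### Post-dose RVNA results below the LLOQ are deleted as missing, so observed low values drop out of the GMCs and the ≥0.5 IU/mL rates; the rule should be replaced, although its effect is probably small

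*SAP*

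**What the plan says.** SAP 2.3.5 sets BLQ results to zero when the sample precedes the injection date. For all other samples, "otherwise, they will be treated as missing data and will not be included in the analysis".

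Two general rules decide what follows:
- SAP 2.3.4: "Missing data are not planned to be handled in this study, unless otherwise specified".
- Protocol 13.5.1: "Unless otherwise stated, missing values will not be included in the calculation of percentage".

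The analyses affected are the Day 8 primary GMC, the Day 4 and Day 99 GMCs, AUEC1-15, and the positive rate at every visit. For the rate, SAP 3.2.2.2.1 states that "inter-group differences in positive rates and their 95% CIs will be calculated based on Wald or Clopper-Pearson". The Day 99 rate is a formal step in SAP 2.4: "If the secondary hypothesis testing 2 is successful, testing of non-inferiority of the test group over the control group in antibody positive rate" is tested. Its criterion in SAP 1.3.3 is "the lower limit of 95% CI of RVNA positive rate (test group/control group) > 0.9".

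The only planned sensitivity analysis of these endpoints on the PPS is of this kind: "a sensitivity analysis will be performed after excluding the deviations in post-dose RVNA from geometric mean concentration", with limits at 3 geometric SDs (SAP 3.2.1.1.3 and 3.2.2.2.3). Neither document gives the LLOQ of the RFFIT. The Protocol's statistical section has no BLQ rule, and SAP section 5 does not list this one among the changes from the Protocol.

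**The concern.** A BLQ result is not an absent measurement. The sample was taken and assayed, and the value is known to be low. Under the three rules together, a subject with a quantifiable 0.3 IU/mL counts as negative, while a subject too low to quantify disappears. The lowest responders are removed because of their outcome. The planned sensitivity analysis takes out further extreme values and restores none.

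The direction depends on the endpoint. On Days 4 and 8, BLQ should fall mainly in the HRIG arm, so deletion raises the HRIG results and works against SYN023. For the two Day 99 non-inferiority tests, deletion favours whichever arm has more BLQ, so it is anti-conservative if that arm is SYN023. In every case the reported GMCs, ratios and rates are wrong once BLQ occurs, and Protocol 2.2 makes their description at each time point an objective.

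The same paragraph needs one wording change. It ties the pre-dose rule to the injection date, but the baseline sample is drawn on Day 1, which is that date (Protocol 11.5). Read literally, a baseline BLQ would also become missing. SAP 2.3.1 shows that before the injection is meant.

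**Working it through.** **Inputs from the documents.** Day 4 ratio 13.75, CV 63.25%; Day 8 ratio 11.9, CV 120.5%; Day 99 GMC ratio 86.94%, CV 17.32%; AUEC ratio 147.55%, CV 142% (SAP 1.3.3; the percentage reading of 86.94 follows the Protocol synopsis). For the control rate, Protocol 13.3 gives "estimated protection level of control group is 98.7"%, planned for Day 15 and used here for Day 99.

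**Assumptions.** LLOQ 0.05 to 0.1 IU/mL (the 0.1 IU/mL baseline cut-off in SAP 2.2 needs an LLOQ no higher); lognormal RVNA; 600/200 evaluable (750/250 less 20%).

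**Plan's own figures.** With log SD σ = √ln(1+CV²), the stated totals of 16 (Day 8), 12 (Day 4), 308 (Day 99 GMC) and 900 (AUEC) reproduce. The values of σ are 0.580 (Day 4), 0.947 (Day 8), 0.172 (Day 99) and 1.051 (AUEC).

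**Days 4 and 8.** Let G be the HRIG GMC and a = ln(LLOQ/G)/σ. The BLQ share is Φ(a). After deletion the mean log is ln G + σφ(a)/(1−Φ(a)).

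Day 4 example, with an assumed SYN023 GMC of 2 and LLOQ 0.1:
- G = 2/13.75 = 0.1455, and a = ln(0.1/0.1455)/0.580 = −0.646.
- The BLQ share is 25.9%.
- The HRIG GMC after deletion is 0.187, so the ratio is 2/0.1874 = 10.67.

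| Visit | SYN023 GMC (assumed) | LLOQ | HRIG BLQ | Ratio after deletion |
|---|---|---|---|---|
| Day 4 (true 13.75) | 2 | 0.1 | 25.9% | 10.67 |
| Day 4 | 5 | 0.05 | 0.03% | 13.7 |
| Day 8 (true 11.9) | 2.5 | 0.1 | 21.7% | 8.36 |
| Day 8 | 4.55 | 0.1 | 7.8% | 10.2 |
| Day 8 | 10 | 0.05 | 0.1% | 11.9 |

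The 4.55 IU/mL is the Day 7 value for SYN023 alone in Protocol 6.3.4. In the least favourable Day 8 row the HRIG rate at or above 0.5 IU/mL moves from 18.0% to 23.0%. SYN023 itself has almost no BLQ.

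**Day 99 rate at the 0.9 boundary.** The control rate is 98.7%, so SYN023 is at 0.9 × 98.7% = 88.83%. The implied GMCs are 0.5·exp(σz), with z the normal quantile of each rate. Error is from 400,000 simulated trials per cell; the table shows the worse LLOQ, 0.1.

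| CV | Implied GMC ratio | BLQ share of SYN023 negatives | Error, ratio interval | Error, difference interval |
|---|---|---|---|---|
| 17.32% | 0.841 | 0% | 2.5% | 2.4% |
| 120.5% | 0.385 | 1.6% | 3.3% | 3.1% |
| 142% | 0.347 | 2.7% | 3.9% | 3.7% |

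- Without deletion, error is 2.5 to 2.6% (log-Wald ratio) and 2.4 to 2.5% (Wald difference). At LLOQ 0.05 it is at most 2.7% with deletion.
- The difference column assumes a margin of 88.83 − 98.7 = −9.87 points. The two larger CVs are borrowed from Day 8 and AUEC.
- The rate test is reached only if the Day 99 GMC test passes (lower limit above 0.8). That probability is 94% at CV 17.32%, where there is no BLQ, and below 0.001 at the larger CVs, where the rate test becomes exploratory.
- If a separate low-responder tail put 10% of all negatives below the LLOQ, error would be about 9.7% (ratio) or 8.6% (difference), before the gate is applied.

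**Day 99 GMC.** The excess SYN023 BLQ share that would hide a fall from 0.8694 to 0.80 is ln(0.8694/0.80)/ln(SYN023 GMC/(LLOQ/2)). For an assumed HRIG GMC of 2 with LLOQ 0.1, this is 0.0832/ln(1.739/0.05) = 2.3%. For 20 with LLOQ 0.05 it is 1.3%. The plan expects only 1.3% of controls (100 − 98.7) to be below 0.5 IU/mL at all.

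**AUEC1-15.** SAP 3.2.2.3 does not say what happens to a curve with a deleted visit. Suppose, as an illustration, that 8% of HRIG subjects are dropped for this reason. Power then falls from 92.8% (600/200) to 91.3% if loss is unrelated to AUEC, and to 81% or 66% if loss has correlation 0.25 or 0.5 with low AUEC.

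**The case against.** The strongest reply is that no confirmatory decision is shown to change. The primary and Day 4 tests have very large margins and the bias runs against SYN023. In the lognormal Day 99 cases, either the gate is closed or there is no BLQ. The low-responder tail has no support in the documents: SYN023 plus vaccine kept 100% protection to Day 84 in SYN023-005 (Protocol 6.3.4). Even with that tail, when 10% of negatives are BLQ, passing both the Day 99 GMC gate and the rate test had probability at most 2.8% with equal main-body GMCs, and did not occur in 3,000 simulated trials per setting at the planned ratio of 0.8694. All of this stands, and it is why the effect is called probably small.

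A second reply is that LLOQ/2 overshoots in SYN023's favour on Day 4: 15.0 against a true 13.75, where substitution at the LLOQ gives 12.6. That is correct. It argues for showing both, not for deletion, which at 10.7 is further from the truth than either.

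A third is that the LLOQ belongs to the central laboratory's documents. It may be recorded there, but a SAP rule that depends on it should still state it.

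The reply that AUEC1-15 was left out of the claim of a small effect is fair. The figures above are only illustrative, and the AUEC effect remains open.

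**Conclusion.** The rule is wrong as written. With the missing-data and percentage rules, it removes observed low results from the GMCs and from the rate denominators, and nothing in the plan puts them back. Confidence in that is high.

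Confidence in the size is low, because neither the LLOQ nor the BLQ frequency is given. Under the stated assumptions the primary decision is safe, the HRIG estimates on Days 4 and 8 may be noticeably too high, and the Day 99 rate error stays at or below 3.9% at the boundary. Larger Day 99 errors need a concentration of unquantifiable results that no part of the documents supports. The exception to calling the effect small is AUEC1-15, where it depends on an unstated handling rule.

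**What to change.** Rewrite SAP 2.3.5 to:
- state the LLOQ of the RFFIT;
- count every post-dose BLQ result as below 0.5 IU/mL, in the denominator, in all rate analyses;
- enter BLQ into the GMC and AUEC1-15 by one prespecified substitution (for example LLOQ/2), with one sensitivity analysis (substitution at the LLOQ, or a left-censored model);
- apply the pre-dose rule by injection time, not injection date;
- reserve missing for samples not taken or not assayable.

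The cost is one paragraph and one sensitivity table before database lock, with no new data. Any substitution is an approximation. In the least favourable Day 4 case the spread is 15.0 (LLOQ/2) to 12.6 (LLOQ) around a true 13.75, and the sensitivity table would show it.

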2.3.6 Handling Rules of Other Data

Only data generated at scheduled visits will be summarized, and the test results at unscheduled visits will not be included in the final analysis, unless otherwise specified. The last non-missing test result will be used for analysis if two or more tests are performed at the same scheduled visit. Results of multiple tests at unscheduled and scheduled visits are present in listings.

2.4 Multiplicity Comparison

Based on multiple hypothesis testing in this study, testing of superiority of the test group over the control group in the geometric mean concentration of RVNA on Day 8 post-dose will be performed at the 0.025 (one-sided) level (testing of primary study hypothesis);

If the primary hypothesis testing is successful, testing of superiority of the test group over the control group in the geometric mean concentration of RVNA on Day 4 post-dose will be performed at the 0.025 (one-sided) level (testing the secondary hypothesis 1), otherwise, testing of all 4 secondary hypotheses will be performed for exploratory analyses;

If the secondary hypothesis testing 1 is successful, testing of non-inferiority of the test group over the control group in the geometric mean concentration of RVNA on Day 99 post-dose (test for the secondary hypothesis 2) will be performed at a level of 0.025 (one-sided), otherwise, testing of secondary hypotheses 2, 3 and 4 will be performed for exploratory analyses;

If the secondary hypothesis testing 2 is successful, testing of non-inferiority of the test group over the control group in antibody positive rate of RVNA ($RVNA \geq 0.5$ IU/mL) on Day 99 post-dose (testing of the secondary hypothesis 3) will be performed at a level of 0.025 (one-sided), otherwise, testing of secondary hypotheses 3 and 4 will be performed for exploratory analyses;

If the secondary hypothesis testing 3 is successful, testing of superiority of the SYN023 plus Rabies Vaccine over the HRIG plus Rabies Vaccine in AUEC₁₋₁₅₀ of

RVNA GMC will be performed at a level of 0.025 (one-sided) (testing of the secondary hypothesis 4), otherwise, testing of secondary hypotheses 4 will be performed for exploratory analysis.

2.5 Subgroup Analysis

If the number of subjects in each subgroup is sufficient, the primary endpoint will be analyzed by the following subgroups:

- 1) Study sites
- 2) Sex
- 3) Age groups (18-59 years, 60 years and older)

2.6 Pooling of Study Sites

All data of the study sites are pooled for a direct integrated analysis, except efficacy analysis, where study sites are as the covariate.

3 Statistical Analysis

3.1 General Information of Subjects

3.1.1 Enrollment and Study Completion

The randomization, completion and early withdrawal of subjects will be described by study sites and overall population:

In the screened population, the number (percentage) of subjects who are randomized and those who are not randomized along with their reasons, and the screening results of all subjects will be tabulated.

Based on the randomized subjects, the number of subjects who included in SS and PPS, those who completed the RVNA blood sampling on Study Days 1, 4, 8, 15, 43, and 99, those who completed the neutralizing activity blood sampling on Day 183 as well as Day 365, those who completed safety observation from Day 1 to Day 99 and from Day 100 to Day 365, and those who prematurely discontinued (including the reasons for premature discontinuation) will be summarized by treatment group. Reasons for premature discontinuation will be tabulated according to the order on the electronic case report form (eCRF). In addition, the study completion status of the randomized subjects will be tabulated.

3.1.2 Protocol Deviation

In order to evaluate whether the protocol is strictly followed, all protocol deviations will be reviewed and assessed in a blinded status according to the contents and protocol requirements before database lock. The study team will assess and classify the deviations as major or minor protocol deviations. Based on the pre-defined SS, the major protocol deviations will be tabulated and summarized.

Based on randomized subjects, all protocol deviations will be tabulated by subjects and study sites.

3.1.3 Demographics and Baseline Characteristics

The demographics and baseline characteristics of subjects will be summarized descriptively based on the PPS and SS by pre-defined groups respectively. Demographics and baseline characteristics will be tabulated.

Demographics:

Categorical variables: sex (male, female), ethnic group (Han, Zhuang, Yi, Hani, Miao, others), and age grouping (18-59 years, 60 years and older).

Continuous variable: age.

Baseline characteristics:

Categorical variables:

- BMI (< 18.5 kg/m², 18.5-24.0 kg/m², ≥ 24.0 kg/m²)
- Type of category III exposure
- Animal causing the wound
- Wound site
 - Category of wound site (high risk, low risk)
- Wound amount
 - Category of wound amount (single wound, multiple wounds)
- Are post-exposure wound cleaning and disinfection performed as required
- Is local anesthesia performed for cleaning and disinfecting the wound
- Did the subject get bitten by animals susceptible to rabies virus during the past 6 months
- Did the subject received any prior/concomitant vaccines 14 days prior to enrollment to the study
- RVNA grouping (RVNA < 0.1 IU/mL and RVNA ≥ 0.1 IU/mL) on Study Day 1

Continuous variable:

Height, weight, body mass index (BMI), and duration from rabies virus exposure to investigational product injection.

It is defined as high-risk if the wound site is any of the head, neck, face, left upper limb, right upper limb; and low-risk for the other parts. Duration of rabies virus exposure to investigational product injection time (h) = investigational product injection time – rabies virus exposure time.

3.1.4 Medical history

Based on the SS, the medical history (including history of past significant disease/ present illness) of subjects will be tabulated and summarized by treatment groups. Medical history will be coded using MedDRA 23.1 or the latest version of coding dictionary prior to database lock, and summarized by System Organ Class (SOC) or Preferred Term (PT).

All the history of past significant disease/ present illness will be tabulated; in addition, history of exposure and bites by animals susceptible to rabies virus will be presented in listing.

3.1.5 Prior/concomitant therapy

3.1.5.1 Prior/concomitant medication

Prior medications are non-investigational medications that stopped prior to the injection of investigational product.

Concomitant medications are all medications (except investigational products and concomitant vaccines) used by the subject within 1-43 days after the subject received the first dose of vaccine and the completion of the passive immunization:

- All medications that started on or after the first vaccination and within 43 days.
- All medications that started before the first dose of vaccine and continued after the first dose.

If the end date of a medication is prior to the date of first vaccination, the medication will be treated as prior medication; if the start date of a medication is on or after the date of first vaccination or the medication is “ongoing”, the medication will be treated as concomitant medication. In addition, if the end date of a medication is not complete, it will be handled according to the rules in the table below.

Table 2 Handling Rules for Missing Dates

Available Part(s)	Missing Parts(s)	Concomitant Medications or Not
[None]	Year, Month, Day	Yes
Month, Day	Year	Yes
Year	Month, Day	Yes, if the year \geq the year of first vaccination date
Month, Year	Day	Yes, if the year $>$ the year of first vaccination date, or if the year = the year of first vaccination date and the month \geq the month of first vaccination date
Day, Year	Month	Yes, if year \geq year of date of first vaccine

Based on the pre-defined SS, medications will be coded using the World Health Organization Drug Dictionary (WHODRUG, version 01-Mar-2020 or latest version at the time of database lock). The number and percentage of subjects with prior/concomitant medications will be calculated by treatment group, anatomical therapeutic class (ATC) level 2, and PN only.

Prior and concomitant medications will be tabulated.

